5.1.2 Descriptive Statistics

All raw and derived variables will be listed and described using summary statistics. For categorical variables, summary statistics will be displayed using descriptive statistics by frequency count and percentages by category. The missing category will be presented if there is at least one missing category for at least one study intervention group. Except otherwise specified, participants with missing data will be included in the calculation of percentages. For quantitative variables, summary statistics will be displayed using descriptive statistics by number of observations, arithmetic mean, SD, median, minimum and maximum and 95% CI if needed. Frequency and proportion of missing data will be displayed.

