5.7.3 Analysis of Key Secondary Pharmacodynamic Endpoints

5.7.3.1 Endpoint, Treatment Effect and Estimand Definition

To assess the secondary objectives, the key secondary endpoints and estimands have the following key attributes:

- Population of interest: healthy adult male participants as defined by the listed inclusion/exclusion criteria in Section 5.1 and 5.2 of the protocol.
- Secondary endpoint of interest:
 - CMAP total amplitude at Week 40, measured as percentage relative to baseline (%), calculated as [value at Week 40 (mean of the three measurements)/baseline value (means of the six measurements)]*100
 - Incidence at Week 28 of recovery of CMAP total amplitude
 - Incidence of recovery of CMAP total amplitude at Week 40

The recovery is considered to be reached for all the visits occurring after the time to recovery, i.e. the first visit for which CMAP total amplitude return to at least 85% of the baseline value.

- ICEs are the following:
 - b) Study discontinuation
 - b1) PDs with potential impact on relevant CMAP total amplitude assessments (i.e. participant received the wrong study intervention and time window violation at the corresponding time point ($> +/- 2$ weeks)),
 - b2) PDs with no expected impact on relevant CMAP assessments (e.g. other time window violations, PDs related to covid-19)
- Treatment regimen: Dysport, Botox or Xeomin will be administered as described in Section 6 of the protocol and potential intake of permitted concomitant medications (for a list see Section 6.8 of the protocol).
- For ICEs (a) and (b1) a hypothetical strategy will be used, the treatment difference which would have been measured if the ICE would not have happened is of interest and will be assessed taking into account the long term pharmacodynamic effect of the investigated compounds. This implies that assessments after the occurrence of a major protocol deviation interfering with CMAP total amplitude will be ignored for the analysis. For CMAP total amplitude at Week 40, no imputation will be done (MMRM analysis). For the incidence of recovery, it will be considered as "No recovery" if the next available percentage CMAP relative to baseline (%) is inferior to 85% and will be imputed to the worst scenario "Recovery" if not or in case of no available CMAP after this ICE.

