5.7.3.2 Main Secondary Analyses

5.7.3.2.1 CMAP Total Amplitude at Week 40

CMAP total amplitude at Week 40 will be analysed using the same MMRM model used for the primary analysis.

5.7.3.2.2 Incidence of Recovery of CMAP Total Amplitude at Week 28 and Week 40

Incidence of recovery of CMAP total amplitude at Weeks 28 and 40 will be analysed for each of the two timepoints by estimating proportion of participants with recovery in each of the treatment arms, p_D in the Dysport arm, p_B in the Botox arm, p_X in the Xeomin arm, as well as the risk differences $p_D - p_B$ and $p_D - p_X$ with point estimates as well as according exact

(Clopper-Pearson) 95% CI for p_D , p_B and p_X and exact unconditional 95% CI for the risk differences.

A Fisher's Exact Test (one-sided, significance level 2.5%) will be used for testing each of the comparisons of Dysport to Botox or Xeomin respectively in the framework of the multiple testing procedure described in [Section 5.7.1.3](#).

5.7.3.3 *Subgroup Analysis*

No subgroup analyses will be performed.

5.7.3.4 *Supplementary Analysis*

In case of occurrence of major PDs with the potential to interfere with CMAP total amplitude ([see section 5.3](#)), a supplementary analysis using the same models used for the main secondary analyses will be conducted using a treatment policy strategy to handle this ICE. All collected data will be taken into account in this supplementary analysis, even when occurring after PDs.

5.7.4 *Analysis of Other Secondary Pharmacodynamic Endpoints*

To further characterise the pharmacodynamic profile of a single intramuscular administration of study intervention at reducing the CMAP total amplitude of the stimulated EDB, the following secondary pharmacodynamic endpoints will be evaluated:

- Time to onset of action defined as first timepoint where EBD CMAP total amplitude is less or equal to 85% of the baseline value
- Time to recovery is defined as the first timepoint when total amplitude returns to at least 85% of the baseline value (the recovery is considered to be reached for all the visits occurring after the time to recovery).
- Duration of response defined as time between time to onset and time to recovery of CMAP total amplitude
- Maximal inhibition (maximal effect) reached defined as the maximal measured inhibition of CMAP amplitude of stimulated EDB

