- Time to maximal effect on the CMAP total amplitude of stimulated EDB defined on an individual basis as the time between baseline and the timepoint of maximal inhibition of CMAP amplitude of stimulated EDB.

All the endpoints defined above will be analysed descriptively only and listed.

Skin temperature and stimulation intensity will be also collected for quality control, described and listed.

5.7.5 *Analysis of Exploratory Endpoints*

The following exploratory endpoint will be analysed using the same MMRM model used for the primary analysis:

- CMAP total amplitude at all timepoints, measured as percentage relative to baseline (%), calculated as [value at the timepoint (mean of the three measurements)/ baseline value (means of the six measurements)]*100.

Graphical representation of adjusted means (SE) coming from the MMRM model will be performed over time by study intervention group.

Latency of M-wave at all timepoints will be analysed descriptively only and listed.

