6 DATA HANDLING

6.1 Visit window

Time window (+/- 2 weeks) is used to calculate the protocol deviations defined as ICE for the analysis.

No other time windows are needed for analyses.

6.2 Unscheduled Visits, Retest, Withdrawal Visit,

All listings will include retests and unscheduled visits, while for the description by visit in the tables, only the scheduled visits according to the protocol will be described.

Unscheduled visit and retest measurements will be used to provide a measurement for a baseline data or endpoint value (e.g. worst value), if appropriate according to their definition.

If a value requires a retest (for vital signs) the closest non-missing reliable value to the scheduled visit will be used in the summary tables.

An assessment will be considered reliable if it is performed without any technical problem and if the result is within the range of likely values.

Participants who have withdrawn early from the study have their last assessment entered as visit 90 in the eCRF. By convention, for these participants, the visit number will be reassigned to the next empty visit number (i.e. if a participant has Visit 1, 2, 3 and 90 entered in the database, the visit number 90 will be reassigned to visit number 4) for summary tables.

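### SAP 5.7.4 gives no value or censoring rule for participants unrecovered at Week 40 or at withdrawal, so its descriptive summaries of time to recovery and duration of response may cover recovered participants only

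*SAP*

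**What the plan says.** SAP 5.7.4 lists these endpoints under an aim that begins "To further characterise the pharmacodynamic profile of a single intramuscular administration of study intervention". It gives two linked definitions: "Time to recovery is defined as the first timepoint when total amplitude returns to at least 85% of the baseline value", and "Duration of response defined as time between time to onset and time to recovery of CMAP total amplitude". The method for the whole list is: "All the endpoints defined above will be analysed descriptively only and listed". Protocol 9.4.3.4 also makes duration of response descriptive.

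SAP 5.1.2 says what descriptive means for a quantitative variable: "summary statistics will be displayed using descriptive statistics by number of observations, arithmetic mean, SD, median, minimum and maximum", with a 95% CI if needed. For absent values it adds only: "Frequency and proportion of missing data will be displayed".

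CMAP is recorded at Day 7 and then every four weeks to Week 40, which is the end of follow-up (SAP 5.7.2.2; Protocol 1.3).

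**The concern.** Duration of response needs a recovery time. A participant still below 85% of baseline at Week 40, or who leaves the study before recovering, has none. All that is known is that the duration exceeds the time observed. A table of n, mean, SD and median has no place for such a value, so unless a rule is added the participant has nothing to contribute.

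Non-recovery by Week 40 is foreseeable. Recovery at Week 40 is itself a key secondary incidence endpoint. Protocol 4.3 reports inhibition still present six months after Dysport 40 U. Protocol 4.2 describes follow-up to 40 weeks as aiming to capture recovery, which does not guarantee it. If one product acts longer, its arm would be expected to lose more participants from its own duration summary, and they would be those with the longest responses. The trial's stated subject is duration of action, so this is the descriptive table a reader would turn to for a figure in weeks.

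**Working it through.** The plan gives no figure for time to recovery or duration, so there is none to reproduce. The check is a search for a rule, followed by a calculation under stated assumptions.

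**1. Is there a rule elsewhere?**
- SAP 5.7.3.1 classifies a participant after an intercurrent event, including as Recovery "in case of no available CMAP after this ICE". That sentence is written for incidence of recovery only. Being unrecovered at Week 40 is not an intercurrent event.
- SAP 6.2 moves the withdrawal assessment: "the visit number will be reassigned to the next empty visit number". This places a visit in summary tables and does not supply a recovery time.
- SAP 7, on derived data, is marked not applicable.
- SAP Appendix A1 reports ongoing items as a minimum duration, but for medications, procedures, medical history and adverse events, not for CMAP response.
- Neither document mentions censoring or a time-to-event method.

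**2. How many participants would have no value?** Assume log-normal recovery times with median m and coefficient of variation CV. Then s = √ln(1 + CV²), and the share unrecovered at Week 40 is 1 − Φ(ln(40/m)/s).
- m = 28, CV 0.2: s = 0.198; ln(40/28) = 0.357; 0.357/0.198 = 1.80; share 3.6%; 15 × 0.036 = 0.5 participants.
- m = 28, CV 0.4: s = 0.385; 0.357/0.385 = 0.93; share 17.7%; 15 × 0.177 = 2.7 participants.

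With 10% withdrawal spread evenly over 40 weeks, the 0.5-2.7 of 15 becomes 1.6-3.5.

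**3. What happens to the median?** With 15 in an arm, no withdrawal and at least 8 recovered, the Kaplan-Meier median is the 8th shortest time. If 4 are unrecovered and left out, the ordinary median of the remaining 11 is the 6th shortest. The more participants an arm loses, the further its median is pulled down.

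**4. Size of the effect on the between-arm difference.** Simulation: 100,000 trials, 15 per arm, same onset time in both arms, equal CV, recovery dated to the next scheduled CMAP visit, follow-up ending at Week 40. Kaplan-Meier results are averaged over trials in which both medians are reached.

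| Assumed medians (weeks) | CV | True difference | Recovered only | Kaplan-Meier |
|---|---|---|---|---|
| 28 vs 20 | 0.2 | 8 | 7.8 | 8.0 |
| 28 vs 20 | 0.4 | 8 | 6.0 | 8.0 |
| 32 vs 24 | 0.2 | 8 | 7.0 | 8.0 |
| 32 vs 24 | 0.4 | 8 | 4.8 | 7.7 |

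The recovered-only difference falls short of the true one by 0.2 to 2.0 weeks for 28 vs 20 (8 − 7.8; 8 − 6.0), and by 1.0 to 3.2 weeks for 32 vs 24 (8 − 7.0; 8 − 4.8). Kaplan-Meier is slightly low in the last row because the median is not reached in about 3% of those trials. Adding the 10% withdrawal moves the differences by at most 0.2 weeks.

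**The case against.** **The SAP nowhere says that unrecovered participants are dropped.** This is correct. A reader might infer that exclusion as missing is the stated rule, but it is only the natural consequence of having no rule. The table shells are a separate document, and descriptive does not rule out Kaplan-Meier. What stands is that the SAP leaves the handling open.

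**Recovery before onset.** A reader might take the definition literally and assign recovery at Day 7 to someone who never fell to 85%. The definition speaks of amplitude that returns to 85%, which already implies a prior fall. The onset wording therefore needs clarifying; it is not an error with a measurable effect.

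**The size rests on assumptions.** This also stands. For medians with equal spread, the gap between recovered-only and Kaplan-Meier differences is at most 2.9 weeks (7.7 − 4.8). That is below the four-week visit spacing, and below or similar to the trial-to-trial SD of the median difference with 15 per arm (about 2.9-4.9 weeks). But imprecision is no reason to accept an avoidable bias as well. Larger distortions can be produced for means, but those true means extrapolate beyond Week 40 and a Kaplan-Meier median would not restore them. A reader might also infer that the contrast could change sign: medians of 28 (CV 0.4) vs 26 (CV 0.2) give −0.2 recovered-only against a true 2 and a Kaplan-Meier value of 2.1. That needs medians close together and a twofold difference in spread, and nothing in the documents supports those inputs.

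**Much is visible anyway.** The missing count, the recovery proportions at Weeks 28 and 40, the listings and the plot of adjusted means let a reader see roughly how many had not recovered. They do not correct the mean or median duration.

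**Conclusion.** The gap is real and should be closed, as an improvement to two descriptive endpoints. SAP 5.7.4 with SAP 5.1.2 leaves participants who are unrecovered at Week 40, or who withdraw unrecovered, without a value or a censoring rule. The likely result is a recovered-only summary.

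The true size is unknown because the documents give no recovery times. Under log-normal recovery with equal CV of 0.2-0.4 and the same onset in both arms, a true 8-week difference in medians shows as 6.0-7.8 weeks (28 vs 20) or 4.8-7.0 weeks (32 vs 24). Kaplan-Meier gives 8.0 and 7.7-8.0.

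Two stronger conclusions are not supported. First, a reader might think the tested results are affected. They are not: both endpoints lie outside the Hochberg sequence, and the MMRM and Fisher tests do not use them. Second, a reader might suspect that the omission favours the sponsor's hypothesis. In the equal-spread scenarios above it shrinks the contrast.

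**What to change.** In SAP 5.7.4:
- Among participants with onset, summarise time to recovery and duration of response by Kaplan-Meier, right-censored at the last CMAP assessment.
- Put event and censoring times on the same scale, either both actual study day or both nominal visit. With visit windows of up to 6 days, mixing the two could place a Week 40 censoring before a Week 40 event. If nominal visits are used, say where the reassigned withdrawal visit of SAP 6.2 falls.
- Report median and quartiles with 95% CI where reached, and the number censored per arm, split into Week 40 and withdrawal.

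In both SAP 5.7.4 and SAP 5.7.3.1, as a clarification, so that the SAP carries one definition:
- State that recovery is the first visit after onset at or above 85% of baseline.
- Report participants with no onset as a separate count, and state how they are classified in the incidence endpoints.
- Footnote the number per arm, withdrawn or no-onset, who are treated differently in the incidence and Kaplan-Meier outputs. With 10% withdrawal and assumed medians of 20-32 weeks, about one withdrawn participant per arm (0.8-1.3 of 15) would count as Recovery at Week 40 and be censored here.

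Keep both endpoints descriptive.

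The cost is SAP wording plus one table and one figure from data already collected. Sample size, alpha and tests do not change. A median may have to be reported as not reached: with 15 per arm and 0-10% withdrawal it is reached in 96-100% of simulated trials at an assumed true median of 32 weeks or less, 80-95% at 36 and 50-53% at 40.

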5.8 Safety

5.8.1 General Consideration

All safety summaries and analyses will be based upon the Safety Set. All safety data will be included in participant data listings (see listing detail conventions in [Appendix A3](#)). There will be no statistical comparison between the study intervention groups for safety data.

Baseline value definition is given in [section 5.1.2](#). Rules to handle multiple observations of the same parameter that occurred for the same visit/timepoint are explained in [section 6.2](#).

5.8.2 Extent of exposure

Participants will receive a single study intervention administration on Day 1, so no derivation of duration of exposure will be done.

A listing will be presented for drug administrations.

5.8.3 Adverse Event

All Adverse Events (AEs) recorded in the eCRF will be coded using the latest version of MedDRA dictionary effective within IPSEN at the time of the database lock. AEs will be classified as Treatment-Emergent AEs (TEAEs) according to the rules below:

- Events with start date and time on or after the date and time of IMP administration,
- Events whose intensity increased on or after the date and time of IMP administration,

Refer to [Appendix A1](#) for handling of partial date. In the case where it is not possible to define an AE as treatment emergent or not, the AE will be classified by the most conservative case, i.e. treatment-emergent.

The following summaries will be provided:

- An overview table summarizing the
 - number and percentage of participants with at least one of the following AEs: any AE; any TEAE; TEAEs by intensity; TEAE by causality; AESIs by type of AESI (hypersensitivity and Remote Spread of Toxin AESIs), related and not related Serious Adverse Event (SAE), treatment-emergent SAE, TEAE leading to discontinuation from the study,
 - corresponding number of events for each of the AE categories listed above,
- A summary of the number and percentage of participants reporting at least one TEAE and the number of events, by study intervention group, SOC and PT,
- A summary of the number and percentage of participants reporting at least one treatment related AE and the number of events, by study intervention group, SOC and PT,
- A summary of the number and percentage of participants reporting at least one TEAE and the number of events, by study intervention group, by decreasing overall frequency of PT.

AEs summaries will be ordered in term of decreasing frequency for SOC and PT within SOC in overall participants and then alphabetically for SOC and PT within SOC.

In the overall summary, only the final adjudicated list of Remote Spread of Toxin AESIs confirmed by the sponsor as “a possible remote spread event” will be included.

In summary presentations, AEs will be counted as follows:

- Participants with more than one AE within a particular SOC are counted only once for that SOC. Similarly, participants with more than one AE within a particular PT are counted only once for that PT;
- Participants reporting a TEAE more than once within that SOC/ PT, the TEAE with the worst-case relationship to study medication (order: related > not related > missing) will be used in the corresponding relationship summaries;
- If the causality is missing for a TEAE, it will be considered related in the summary tables.

In addition, a listing with all AEs data will be listed by study intervention group including non-TEAEs, Treatment-emergence status will be flagged in the listing.

A specific listing will be performed for treatment-related AEs.

Deaths, SAEs, and Other Significant Adverse Events (AE)

AESIs for Dysport are TEAEs that suggest a possible remote spread of effect of the toxin or events suggestive of hypersensitivity-like reactions.

- TEAEs due to possible remote spread of the effects of Dysport will be identified using the list of MedDRA PTs compatible with the mechanism of action of Dysport and based on the FDA.
- TEAEs potentially representing hypersensitivity reactions will be identified using the Standardised MedDRA Query (SMQ) (narrow search query) for hypersensitivity reactions.

The list of MedDRA preferred terms, used to identify any potential AESI, is provided in the data review plan.

All potential Remote Spread of Toxin AESIs identified using the search strategy described above will be medically evaluated during the study, before the database lock and unblinding, by the sponsor to identify events which could possibly represent 'remote spread of effect of toxin' due to study treatment administration. Potential Remote Spread of Toxin AESIs will be excluded if they are confounded by presence of alternative clinical aetiologies (medical history, concomitant medication or diagnosis which could account for the symptoms); if they are considered to be local effects instead of remote spread of toxin as judged by the site of injection; the time period between the last study treatment administration and event onset is not in accordance with the expected mechanism of action; or due to insufficient information/evidence to make an assessment.

The following summary tables on AESIs will be performed:

- AESIs with the number and percentage of participants and the number of events presented by study intervention group, by primary SOC and PT, presented by type of AESI (hypersensitivity and Remote Spread of Toxin AESIs).
- In addition, a table of pre-adjudicated potential Remote Spread of Toxin events will be produced for transparency and traceability by study intervention group and by primary SOC and PT.

The following listings will be provided:

- A listing of all deaths that occurred during the study,
- A listing of all SAEs,
- A listing of all AEs leading to discontinuation of study,
- A listing of participants having AESIs.

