10.3.3 Recording and Follow-Up of AE and/or SAE

AE and SAE Recording

- When an AE/SAE occurs, it is the responsibility of the investigator to review all documentation (e.g. hospital progress notes, laboratory reports, and diagnostics reports) related to the event.
- The investigator will then record all relevant AE/SAE information.
- It is **not** acceptable for the investigator to send photocopies of the participant's medical records to the sponsor in lieu of completion of the required forms.
- There may be instances when copies of medical records for certain cases are requested by the sponsor. In this case, all participant identifiers, with the exception of the participant number, will be redacted on the copies of the medical records before submission to the sponsor.
- The investigator will attempt to establish a diagnosis of the event based on signs, symptoms, and/or other clinical information. Whenever possible, the diagnosis (not the individual signs/symptoms) will be documented as the AE/SAE.

Assessment of Intensity

The investigator will make an assessment of intensity for each AE and SAE reported during the study and assign it to one of the following categories:

- Mild: An event that is easily tolerated by the participant, causing minimal discomfort and not interfering with everyday activities.
- Moderate: An event that causes sufficient discomfort to interfere with normal everyday activities.
- Severe: An event that prevents normal everyday activities. An AE that is assessed as severe should not be confused with an SAE. Severe is a category utilised for rating the intensity of an event; both AEs and SAEs can be assessed as severe.

An event is defined as 'serious' when it meets at least one of the predefined outcomes as described in the definition of an SAE, NOT when it is rated as severe.

Assessment of Causality

- The investigator is obligated to assess the relationship between study intervention and each occurrence of each AE/SAE.
- A "reasonable possibility" of a relationship conveys that there are facts, evidence, and/or arguments to suggest a causal relationship, rather than a relationship cannot be ruled out.
- The investigator will use clinical judgment to determine the relationship.
- Alternative causes, such as underlying disease(s), concomitant therapy, and other risk factors, as well as the temporal relationship of the event to study intervention administration will be considered and investigated.

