2.3 Sample Size Determination and Power

It was anticipated that approximately 48 participants are planned to be screened to achieve 15 participants randomised to Dysport, 15 participants randomised to Botox and 15 participants randomised to Xeomin using a 1:1:1 randomisation ratio and assuming a screening failure rate of 5%.

The sample size calculation is based on the primary efficacy estimand and its endpoint relative change from baseline in EDB CMAP total amplitude at Week 28. Using a 2-sided t-test at the 5% significance level, the chosen sample size provides at least 88% power to detect a treatment difference of 18% relative change from baseline in the Dysport arm than in a comparator arm assuming a common Standard Deviation (SD) in all treatment arms of 15% as observed for Dysport in a legacy study [CCI](#) – Part B. The treatment difference is based on the observed average EDB CMAP total amplitude at 6 months of Dysport 40 U ([CCI](#) – Part B) and of Botox and Xeomin 16 U in Wohlfarth [[Wohlfarth 2007](#)]. The power analysis was conducted with NQuery version 8.4.1.0. Given the made assumptions and the sample size of 15 participants per arm the probability to show superiority of Dysport to both comparators simultaneously is at least 81%, as shown in a simulation study conducted with software R version 4.0.3.

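### SAP 5.8.3 ranks missing causality below not related, then counts it as related, and does not say which rule is applied first

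*SAP*

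**What the plan says.** SAP 5.8.3 introduces its counting rules with "In summary presentations, AEs will be counted as follows". Two of the bullets that follow deal with relationship to study medication.

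- For a participant who reports a TEAE more than once within a SOC/PT, "the TEAE with the worst-case relationship to study medication (order: related > not related > missing) will be used in the corresponding relationship summaries". Missing is the lowest of the three levels.
- The next bullet reads "If the causality is missing for a TEAE, it will be considered related in the summary tables". Here missing is placed at the highest level.

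The same section plans two outputs that use causality. One is a table broken down by SOC and PT within each arm: "A summary of the number and percentage of participants reporting at least one treatment related AE and the number of events". The other is the overview table, whose rows include "any AE; any TEAE; TEAEs by intensity; TEAE by causality". Protocol 9.4.4 also plans treatment-related AE tables by SOC and PT with participant and event numbers, but gives no rule for missing causality. Neither document says whether the ranking or the recoding is done first.

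**The concern.** The two rules give missing causality opposite weights, and the result for some participants depends on their order. The words placing missing last in the ranking have a function only if missing values are still present when the worst case is selected, that is, if the ranking comes first. A programmer who works through the bullets in their printed order would do that.

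Ranking first is also the less cautious choice. It lets a known not-related event displace an event of unknown relationship, so any discrepancy lowers the number of participants with treatment-related AEs. That runs against the second bullet. It also runs against the approach earlier in the same section, where an AE that cannot be classified as treatment-emergent or not is taken as treatment-emergent.

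What is at stake is the participant column of the treatment-related table and, if it is programmed from the same selection, the causality rows of the overview.

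**Working it through.** The plan states no figure to reproduce here. The check is to apply both orders to every possible case.

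**Inputs**
- Ranking: "worst-case relationship to study medication (order: related > not related > missing" (SAP 5.8.3).
- Recoding: missing becomes related in summary tables (SAP 5.8.3, next bullet).
- Planned arm size: "15 participants randomised to Dysport, 15 participants randomised to Botox and 15 participants randomised to Xeomin" (SAP 2.3).

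**Notation.** R = related, N = not related, M = missing, for the TEAEs of one participant within one SOC/PT.
- Order A: select the worst case by R > N > M, then recode a selected M to R.
- Order B: recode every M to R, then select the worst case.

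**Number of cases.** With three levels, the number of distinct combinations of k events is (k+1)(k+2)/2. This gives 3 for k = 1, 6 for k = 2 and 10 for k = 3, so 3 + 6 + 10 = 19.

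**Result.** The two orders agree in 16 of the 19 combinations and disagree in 3:

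| Events | Order A | Order B | Related events if each M is recoded |
|---|---|---|---|
| N+M | not related | related | 1 |
| N+N+M | not related | related | 1 |
| N+M+M | not related | related | 2 |

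The orders agree for any single event (M alone ends as related under both), for any set that contains an R, and for sets that are all N or all M. The disagreement therefore needs at least one N, at least one M and no R.

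**Event counts.** If the recoding is applied to each event, the last column is the same under both orders. Under order A, an N+M participant could add one related event to a row of the table without being counted as a participant with a related AE in that row.

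**Step size.** One reclassified participant changes an arm's percentage for that SOC/PT by 1/15 = 6.7 points. The Safety Set is classified by treatment received (SAP 4), so the actual denominator may differ from the planned 15. With 14 the step would be 1/14 = 7.1 points, and with 16 it would be 1/16 = 6.3 points.

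**Frequency.** The documents give no rate of missing causality, so the expected number of affected participants cannot be derived.

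**The case against.** The best defence is that the recoding bullet has no exceptions and works at the level of the single event. On that reading a missing causality is already related in any summary table, the worst case of N and M is R, and the mention of missing in the ranking is merely redundant. The two named outputs also count participants with at least one event of a kind, which needs no worst-case selection, and no listed table is described as putting each participant into a single causality category. The table shells are a separate document, so an effect on an actual output cannot be shown from the SAP alone.

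Much of this stands. A reader might infer that the SAP, applied as written, undercounts treatment-related AEs. The documents do not support that: the undercount arises only if the ranking is done first, and the text does not require that order. A reader might also infer that all treatment-related counts depend on the order. They do not, since event counts need not change and most combinations give the same answer.

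The defence does not remove the ambiguity. The SAP says the ranked TEAE will be used in the relationship summaries, and the treatment-related table by SOC and PT is such a summary. If the recoding always comes first, the SAP contains a ranking level that can never be used, and nothing tells the programmer so.

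The trigger should also be rare. Protocol 10.3.3 states: "The investigator is obligated to assess the relationship between study intervention and each occurrence of each AE/SAE". Protocol 10.1.8 requires reasons for missing data and queries on unexplained items. SAP 5.8.1 rules out statistical comparison of safety data, and the full AE listing would make any case traceable.

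**Conclusion.** The inconsistency is real but minor. As the SAP stands, a participant with at least one not-related TEAE, at least one TEAE of missing causality and no related TEAE in the same SOC/PT can be classified either way. The consequence is limited to numbers and percentages of participants with treatment-related AEs, at about 6.7 points per affected participant for that term and arm. That is the step for one participant with 15 in the arm, not an expected effect. No pharmacodynamic endpoint is touched. The conclusion assumes that the ranking feeds the treatment-related summary, as its wording indicates, and that the table shells do not already fix the order.

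**What to change.** In SAP 5.8.3, move the missing-causality bullet ahead of the worst-case bullet, state that missing causality is set to related before the worst case is selected, and reduce the ranking to related > not related. Every combination that contains a related or missing event is then classified as related, only all-not-related sets stay not related, and the participant and event columns agree. The cost is a few words in the SAP and a check that the table shells follow the same order, best done before database lock and unblinding. No data collection or design element changes.
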